9.2. Case Report Forms and Source Documentation

Data obtained during this clinical trial should be promptly entered in the electronic CRF (eCRF). All source documents from which eCRF entries are derived will be placed in the subject's medical records. An eCRF will be completed for every subject who was screened for participation in the clinical trial. Measurements for which source documents are available include vital signs, physical exams, laboratory assessments and ECG recordings.

A representative of the Sponsor or designee (a Site Monitor) will visit the clinical trial center periodically to monitor adherence to the protocol and to applicable regulatory regulations, and the maintenance of adequate and accurate clinical records. The eCRFs will be reviewed in detail, for which the Site Monitor will have access to subject medical records, laboratory data, and other source documentation. Remote monitoring may be utilized in some circumstances. The Site Monitor will make a decision as to their acceptability. If errors or omissions are found in the course of a data review, or if clarification of data is required, the eCRFs in question will be corrected by the Investigator or designee.

After full review by the Site Monitor and resolution of any data clarifications, the Investigator will sign and date the completed eCRF. This signature will indicate that thorough inspection of the data therein has been made and will thereby certify the contents of the form.

9.3. Access to Source Data

During the course of the clinical trial, Sponsor representatives, Site Monitors, Regulatory authorities, Ethics Committees (ECs), and/or the Sponsor's Quality Assurance Group or designee must have direct access to source data to review protocol compliance, compare CRFs and individual subject's medical records, assess drug accountability, and ensure that the clinical trial is being conducted according to pertinent regulatory requirements. CRF entries will be verified with source documentation. The review of medical records will be performed in a manner to ensure that subject confidentiality is maintained. The Investigator will ensure that the Sponsor is provided with all necessary support at all times.

9.4. Data Processing

All data will be entered using an appropriate data entry system, following standard procedures.

The data review and data-handling document will include specifications for consistency and plausibility checks of data and will also include data-handling rules for obvious data errors.

9.5. Archiving Clinical Trial Records

According to ICH guidelines, essential documents will be retained for a minimum of 2 years after the last approval of a marketing application in an ICH region.

It is the responsibility of the Investigator and clinical trial staff to maintain a comprehensive and centralized filing system of all clinical trial-related documentation. This centralized file should be available for inspection at any time by the Sponsor, Site Monitor or the Sponsor's Quality Assurance staff or designee for monitoring or auditing by the Sponsor and regulatory authorities. Elements of clinical trial documentation will include:

- Subject files containing the completed eCRF supporting source documentation and the signed informed consent form (ICF).
- Clinical trial files, containing the protocol with all amendments, the Investigator Brochure, copies of all clinical trial documentation, and all correspondence to and from the EC and the Investigator.
- Pharmacy files, containing the Study Medication Accountability Records or dispensation logs and all clinical trial agent-related correspondence.

9.6. Good Clinical Practice

The procedures set out in this clinical trial protocol are designed to ensure that the Sponsor and Investigator abide by the principles of the eGCP guidelines of the ICH and applicable federal/national and local regulations. The clinical trial also will be carried out in keeping with local legal requirements.

9.7. Informed Consent

Before each subject is screened, written informed consent must be obtained from the subject. The consent forms must be signed and dated and retained by the Investigator as part of the clinical trial records. The Investigator will not undertake any investigation specifically required for the clinical trial until valid consent has been obtained. The terms of the consent and when it was obtained must also be documented in the CRF. Each subject will receive a fully signed copy of each consent form that he/she signs for the clinical trial.

If a protocol amendment is required, the ICF may need to be revised to reflect the changes to the protocol. If the consent form is revised, it must be reviewed and approved by the appropriate EC and signed by all subjects subsequently enrolled in the clinical trial, as well as those currently enrolled in the clinical trial.

9.8. Protocol Approval and Amendment

Before the start of the clinical trial, the clinical trial protocol and/or other relevant documents will be approved by the EC in accordance with legal and regulatory requirements. The Sponsor must ensure that all ethical and legal requirements have been met before the first subject is screened for the clinical trial.

The procedures outlined in the protocol and eCRFs will be reviewed by the Investigator and staff prior to clinical trial initiation to ensure appropriate interpretation and implementation. No deviations from the protocol should be made except in emergency situations in which alternative treatment is necessary for the protection, proper care, and well-being of subjects.

To alter the protocol, amendments must be written, and approvals must be received from the appropriate personnel. Amendments will originate from Sponsor and will be provided to the Investigator for submission to the EC for review and approval prior to implementation. If a protocol amendment substantially alters the clinical trial design or increases potential risk to the study subject, the ICF should be revised and, if applicable, subject's consent to continue participation should be obtained.

Administrative changes may be made without the need for a formal amendment.

9.9. Study Medication Accountability

9.9.1. Handling of Study Medications

The Investigator shall take adequate precautions, including storage of the study medications in a securely locked, substantially constructed cabinet or other securely locked, substantially constructed enclosure, access to which is limited, to prevent theft or diversion of the substances into illegal channels of distribution.

9.9.2. Disposition of Study Medications

The Investigator is required to maintain adequate records of the disposition of the study medications, including dates, quantity, and use by subjects. If the investigation is terminated, suspended, discontinued, or completed, the Investigator shall return the unused supplies to the Sponsor or designee or dispose in accordance with established site procedures. When the Sponsor has indicated in writing that study medication is to be destroyed on site, destruction must be in accordance with local regulations for the product type and a destruction certificate must be provided to the Sponsor.

9.9.3. Premature Termination of the Clinical Trial

The Sponsor reserves the right to terminate this clinical trial at any time. If the clinical trial is terminated prior to scheduled completion, the Investigator will be notified and given any necessary instructions concerning final examinations that are required. If the Investigator, the Sponsor, or the Sponsor's Medical Monitor becomes aware of conditions or events that suggest a possible hazard to subjects if the clinical trial continues, the clinical trial may be terminated after appropriate consultation with the relevant parties.

9.10. Confidentiality

All clinical trial findings and documents will be regarded as confidential. The Investigator and members of his/her research team must not disclose such information without prior written approval from the Sponsor.

The anonymity of participating subjects must be maintained, and national requirements and guidelines must be followed. Subjects will be identified on eCRFs and other documents by their subject number, sex and/or birth date, not by name and subject to local requirements. Documents that identify the subject (e.g., the signed informed consent) must be maintained in confidence by the Investigator.

9.11. Publication Policy

By signing the clinical trial protocol, the Investigator agrees with the use of results of the clinical trial for the purposes of national and international registration, publication, and information for medical and pharmaceutical professionals. If necessary, the authorities will be notified of the Investigator's name, address, qualifications, and extent of involvement.

All information not previously published concerning CST-103 and/or CST-107 and the Sponsor's operations, including, but not limited to, patent applications, formulas, manufacturing processes, basic scientific data, and formulation information, supplied by the Sponsor to the Investigator is considered confidential and shall remain the sole property of Sponsor. The Investigator agrees to use and maintain the confidentiality of this information in accordance with the provisions contained in the clinical trial agreement. Any use or reproduction thereof, including, but not limited to, publications or presentations by the Investigator or his/her associates, must be submitted to the Sponsor for review and approval in accordance with the provisions contained in the relevant agreement governing the conduct of this trial. All publications must acknowledge the sponsorship of Sponsor.

## 1. ABBREVIATIONS

A $\beta$	amyloid- $\beta$
$\alpha$ -syn	$\alpha$ -synuclein
$\beta$ -AR	Beta-adrenoceptor
$\beta$ -hCG	Beta human chorionic gonadotropin
AD	Alzheimer's Disease
AE	Adverse event
ATT	Adaptive tracking test
AUC inf	Area under the drug concentration-time curve from time zero to infinity
AUC t	Area under the drug concentration-time curve from time zero to time t
BMI	Body mass index
BP	Blood pressure
CANTAB	Cambridge Neuropsychological Test Automated Battery
CBF	Cerebral blood flow
CF	Cognitive fluctuations
cGCP	Current Good Clinical Practice
CLIN-001	CST101/CST107-CLIN-001
CLIN-002	CST103/CST107/CST109-CLIN-002
CLIN-003	CST101/CST103/CST109-CLIN-003
C max	Maximum concentration
CNS	Central nervous system
CRF	Case report form
CK	Creatinine kinase
C-SSRS	Columbia-Suicide Severity Rating Scale
CST-103	Clenbuterol HCl
CST-107	Nadolol
CV	Coefficients of variation
DCFS	Dementia Cognitive Fluctuation Scale
DLB	Dementia with Lewy Bodies
DSST	Digital Symbol Substitution Test
EC	Ethics Committee
eCRF	Electronic case report form
ECG	Electrocardiogram
EEG	Electroencephalogram
ERP	Event Related Potential
ESS	Epworth Sleepiness Scale
EW	Early withdrawal
FAS	Full analysis set
FERT	Facial Expression Recognition Task
FOG	Freezing of Gait
FOG-Q	Freezing of Gait Questionnaire
FSH	Follicle-stimulating hormone
GDS	Geriatric Depression Scale
HADS	Hospital Anxiety and Depression Scale
HR	Heart rate
HbsAb	Hepatitis B surface antibody
HbsAg	Hepatitis B surface antigen

Sponsor: CuraSen Therapeutics, Inc.  
Protocol Number: CST103/CST107-CLIN-011  
Version and Date: █████ v1.0 / 24May2022

HCV Ab	Hepatitis C antibody
HIV	Human immunodeficiency virus
HRV	Heart rate variability
IB	Investigator Brochure
ICF	Informed consent form
ICH	International Council for Harmonisation
IRT	Interactive response technology
ITT	Intent to treat
IV	Intravenous
MCI	Mild cognitive impairment
MedDRA	Medical Dictionary for Regulatory Activities
MHYS	Modified Hoehn & Yahr Scale
MoCA	Montreal Cognitive Assessment
MRI	Magnetic resonance imaging
NDD	Neurodegenerative disease
PAL	Paired Associates Learning
PD	Parkinson's Disease
PDD	Parkinson's Disease Dementia
PI	Principal Investigator
PK	Pharmacokinetic
PKS	PK set
PLR	Pupillary Light Reflex
PO	By mouth/oral administration
PPS	Per protocol set
QD	Once daily
RBD1Q	REM Sleep Behavior Disorder Single-Question Screen
RBD+PD	REM Sleep Behavior Disorder positive Parkinson's Disease
RTI	Reaction Time Index

## 2. INTRODUCTION

The statistical analysis plan (SAP) details the planned analysis required to satisfy the Clinical Study Report (CSR) of study number CST103/CST107-CLIN-011: A Phase II, Randomized, Placebo-Controlled, Double-Blind, Crossover Study of the Pharmacodynamic Effects of CST-103 co-administered with CST-107 on the Central Nervous System in Subjects with Neurodegenerative Disorders.

The content of this SAP is based on the protocol version 6.0 (Amendment 6 AUS-NZ) dated 18-Feb-2022 and protocol version 7.0 (Amendment 7 UK-EU) dated 18-Feb-2022 and CRF version 6.0 dated 27-Mar-2022.

### 2.1. Changes from the Protocol

While two separate protocols govern the trial in Australia/New Zealand and the United Kingdom/European Union, all analyses will be performed cumulatively among subjects across all regions, except for BioStamp and SART analyses which are only collected on subjects from Australia and New Zealand.

Additionally, the protocol states that approximately 20 subjects will be enrolled in Cohort A with RBD+PD or MCI and approximately 20 subjects will be enrolled in Cohort B with PDD or DLB. Due to the difficulty in recruiting patients with DLB and PDD the majority of the subjects recruited will be in Cohort A and the majority of these are RBD+PD subjects. Cohort B data will be captured in listings and summarized in the demographics, disposition, secondary endpoint analyses, and exploratory analyses tables.

## 3. STUDY OBJECTIVES AND ENDPOINTS

Objectives	Endpoints
Primary	

The primary objective of this study is to identify a CNS signal in one of the planned pharmacodynamic measures after multiple oral doses of CST-103 in the presence of CST-107 in four populations of subjects with Neurodegenerative Disorders (NDD):
 
Cohort A
 
 
1. Parkinson’s Disease (PD) with REM Sleep Behavior Disorder (RBD) and Depressive Symptoms
 
2. Mild Cognitive Impairment (MCI) with Depressive Symptoms
 
 
Cohort B
 
 
1. Dementia with Lewy Bodies (DLB) with Cognitive Fluctuations
 
	
The primary endpoints include:
 
Cohort A:            Change in Negative Emotional Bias in the Facial Expression Recognition Task
 
Cohort B:            Cognitive Fluctuations as measured by:
 
 
1. Spectral analysis of waking EEG
 
2. AUS/NZ Subjects Only: Activity Tracking
 
3. Pupillometry
 
4. Dementia Cognitive Fluctuation Scale (DCFS)
 

2. Parkinson’s Disease Dementia (PDD) with Cognitive Fluctuations
 
These pharmacodynamic assessments will compare the effect of CST-103 co-administered with CST-107 with that of placebo on the following:
 
Cohort A:
 
 
• Emotional Facial Processing
 
 
Cohort B:
 
 
• Cognitive fluctuations
 
	

Secondary
	

The secondary objectives for all subjects include the comparison of the effect of CST-103 co-administered with CST-107 with that of placebo on the following:
 
 
1. Cognition
 
2. AUS/NZ Subjects only: Movement and time spent sitting, standing and sleeping
 
3. Sleep
 
4. Pupillary reactivity
 
5. Mood Assessment
 
6. Safety and tolerability of CST-103 co-administered with CST-107
 
7. The pharmacokinetic (PK) profiles of CST-103 and CST-107
 
	
The secondary endpoints will compare the effect of CST-103 co-administered with CST-107 with that of placebo on the following:
 
 
1. Verbal fluency test (alphabet & category)
 
2. CANTAB cognitive assessments, with include the following:           
 
• Reaction Time (RTI)
 
• Rapid Visual Information Processing (RVP)
 
• Verbal Recognition Memory (VRM) Phase I
 
• Adaptive Tracking Task (ATT)
 
• Paired Associated Learning Task (PAL)
 
• Stop Signal Task (SST)
 
• Delayed Verbal Recall
 
 
 
3. AUS/NZ Subjects Only: Digital wearable device (BioStamp) data, which includes four key measures of interest:           
 
a) Activity and posture classifications, durations, and temporal patterns
 
b) Sleep (duration, posture transitions, and activity counts)
 
c) Autonomic function – heart rate variability (HRV)
 
d) Temporal pedometry (daily step count, and gait cadence)
 
 
 

	
 
4. Assessment of sleep using the digital device and Epworth Sleepiness Scale (ESS)
 
5. Change in pupillary diameter as measured using the pupillary light reflex test
 
6. Geriatric Depression Scale (GDS), Hospital Anxiety and Depression Scale (HADS)
 
7. Adverse events (AE), electrocardiograms (ECGs), vital signs, laboratory safety tests (hematology, chemistry, and urinalysis)
 
8. Plasma PK parameters of CST-103 and CST-107 (including <math>C_{max}</math>, <math>t_{max}</math>, <math>AUC_t</math>, <math>AUC_{inf}</math>, <math>t_{1/2}</math>)
 

Exploratory	

The exploratory objectives are:
 
 
1. To characterize the effect of CST-103 co-administered with CST-107 on inflammatory biomarkers in blood, such as C-reactive protein and cytokine levels.
 
2. To characterize the effect of CST-103 co-administered with CST-107 on neurodegenerative biomarkers in the blood study as neurofilament light chain, total and phosphorylated tau protein, and amyloid-<math>\beta</math> (<math>A\beta</math>) peptides may also be measured
 
3. To characterize the effect of CST-103 co-administered with CST-107 on performance of a sustained attention task in subjects in Cohort B
 
4. To characterize the effect of CST-103 co-administered with CST-107 on Freezing of Gait (FOG) (for subjects with RBD+PD, PDD, and DLB).
 
5. To characterize the locus coeruleus volume and contract ratio (this is an optional objective based on imaging capabilities)
 
	
The exploratory endpoints are:
 
 
1. Changes in inflammatory biomarkers, such as C-reactive protein and cytokine levels, as measured prior to and after CST-103 co-administered with CST-107 may be determined.
 
2. Changes in neurodegenerative biomarkers, such as neurofilament light chain, total and phosphorylated tau protein, and amyloid-<math>\beta</math> (<math>A\beta</math>) peptides, as measured prior to and after CST-103 co-administered with CST-107 may be evaluated.
 
3. AUS/NZ Subjects Only: Performance on the Sustained Attention Response Task (SART) as measured prior to and after CST-103 co-administered with CST-107.
 
4. Assessment of FOG using the FOG-Q (for subjects with PBD+PD, PDD, and DLB).
 
5. The characterization of the brain imaging signal in the locus coeruleus complex using neuromelanin-sensitive MRI sequence. This is an optional
 

Sponsor: CuraSen Therapeutics, Inc.  
Protocol Number: CST103/CST107-CLIN-011  
Version and Date: [REDACTED] v1.0 / 24May2022

	endpoint based on imaging capabilities.
--	---

## 4. STUDY DESIGN

### 4.1. Study Design and Population

[figure not shown]
This is a Phase II, randomized, placebo-controlled, double-blind, crossover study on the CNS and pharmacodynamics effects of CST-103 co-administered with CST-107 in 4 subject populations with Neurodegenerative Disorders at up to ten clinical sites in Australia, New Zealand, and the United Kingdom.

Approximately 40 subjects will be enrolled in a 2 period, 2-way cross over design following study eligibility confirmation during the screening period. The number of subjects enrolled in each cohort may change as emerging data are reviewed from this and other studies. As noted in section 2.1, the majority of the subjects will be in RBD+PD group in Cohort A.

[figure not shown]
During each treatment period, subjects will receive daily doses of 80 µg CST-103 (administered as two 40 µg capsules) co-administered with 1 mg CST-107 (administered as one 1 mg capsule) or matching placebos for 14 days. Each treatment period will be separated by a washout period of 14 days (+5 day window)

The study duration will be approximately 12 weeks, which includes a Screening period of up to 21 days, a Lead-In Period of up to 14 days, the treatment/study period of 6 weeks (two 2-week treatment periods separated with a 2-week wash-out), and the Follow-Up Visit 2 weeks after the last study drug dose.

*Study Schema – Cohort A in RBD+PD or MCI Subjects\**

*Study Schema – Cohort B in DLB or PDD Subjects\**

*\*Biostamp devices will only be used for the Australia/New Zealand subjects but not for the UK or Belgian subjects.*

## 4.2. Randomization and Blinding

The designated Interactive Response System (IRT) will be used to randomize subjects into the study on the first day of the Lead-In Period. Eligible subjects will be randomly assigned in a 1:1 ratio to one of the following two treatment sequences (CST-103/CST-107 to placebo or placebo to CST-103/CST-107). The IRT will provide the randomization number.

Randomization will be stratified by the following factors:

- Disease Criteria:

Sponsor: CuraSen Therapeutics, Inc.  
Protocol Number: CST103/CST107-CLIN-011  
Version and Date: ██████ v1.0 / 24May2022

- Cohort A: PBD+PD or MCI
- Cohort B: DLB or PDD
- Sex (Male vs Female)

This clinical trial is a double-blinded study, with the Sponsor, subjects, and site personnel (e.g., study nurses, coordinators, investigators) blinded to treatment assignment. Limited staff will have access to treatment assignments, such as the unblinded statistical team, IRT system administration, and drug supply management team. Limited CuraSen staff or designees who are not otherwise involved in study conduct may be unblinded during study to evaluate accruing data.

CST-103 40 µg-matched placebo and CST-107 1 mg-matched placebo will be packaged and color-, size- and shape-matched to be indistinguishable from CST-103 40 µg and CST-107 1 mg.

#### 4.3. Sample Size Considerations

A total of approximately 40 subjects is planned in this crossover study. The sample size for the study parts are based on practical considerations. No formal hypothesis testing is planned.

The crossover design allows for an increased level of precision in estimates as compared to a parallel design with the same number of subjects. For primary and cognition related secondary endpoints, a sample size of 20 subjects in each cohort provides at least 80% power in this cross-over design to detect a treatment difference of  $0.79*SD$  (active versus placebo) or larger for each endpoint of interest, where SD represents the standard deviation for the endpoint of interest.

For cognition related secondary endpoints, a sample size of 40 subjects overall (both cohorts combined) provides at least 80% power in this cross-over design to detect a treatment difference of  $0.54*SD$  (active versus placebo) or larger for each endpoint of interest. Sample size assumptions were based on a 2-sided t-test with a Type I error rate of 5%, equal (or no) carryover effects, and a correlation of at least 0.3 between study periods. No adjustments were made for dropouts or multiplicity.

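### SAP 4.3 still gives 80% power on primary endpoints for 20 subjects in each cohort, although the SAP expects a small Cohort B and makes no primary treatment comparison there on activity, pupillometry or DCFS

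*SAP*

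**What the plan says.** SAP 4.3 repeats Protocol 8.1: for primary and cognition-related secondary endpoints, "a sample size of 20 subjects in each cohort provides at least 80% power" to detect 0.79 SD, active versus placebo. The assumptions are a two-sided t-test at 5%, equal or no carryover, and "a correlation of at least 0.3 between study periods". No allowance is made for dropout or multiplicity. The same section says that the size was chosen on practical grounds and that no formal hypothesis testing is planned. It gives the total as about 40 and, unlike Protocol 8.1, no longer splits it 20 and 20.

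SAP 2.1 reports a change: "Due to the difficulty in recruiting patients with DLB and PDD the majority of the subjects recruited will be in Cohort A". SAP 4.1 repeats that "the majority of the subjects will be in RBD+PD group in Cohort A" and adds that "The number of subjects enrolled in each cohort may change as emerging data are reviewed". Neither section gives an expected number for Cohort B.

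On analysis, SAP 2.1 says "Cohort B data will be captured in listings and summarized in the demographics, disposition, secondary endpoint analyses, and exploratory analyses tables"; primary endpoint tables are not among those named. SAP 8.1 says that Cohort B's primary data will only be listed, and gives the small sample as the reason. Its paragraphs on activity tracking, pupillometry and DCFS each specify listings. Waking EEG (Cohort B) and FERT (Cohort A) are referred to separate analysis plans.

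SAP 3 keeps the primary objective for all four disease populations. It states that "These pharmacodynamic assessments will compare the effect of CST-103 co-administered with CST-107 with that of placebo", and names cognitive fluctuations as the target in Cohort B.

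**The concern.** A sample-size section should describe the trial that the plan expects to run. Here the per-cohort sentence rests on 20 subjects in each cohort, while other sections of the same document say that enrolment will be uneven and that the smaller cohort is too small for more than listings of its primary data. SAP 3 and 4.3 read together describe a primary comparison in Cohort B with at least 80% power. SAP 8.1 makes no such comparison for three of Cohort B's four primary endpoints.

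What is at stake is reporting. If the two sections pass unchanged into the study report, the absence of a Cohort B signal could be taken as a finding from an adequately sized comparison. No estimate or p-value in the SAP depends on the sentence.

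**Working it through.** **Inputs.** From SAP 4.3: two-sided α = 0.05, t-test, difference 0.79 SD with 20 subjects per cohort, difference 0.54 SD with 40 subjects pooled, correlation ρ at least 0.3. From SAP 4.2: 1:1 allocation to the two sequences. Cohort B's n is not stated, so it is assumed and a range is shown.

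**Formula.** The SD of the within-subject difference is SD × √(2(1 − ρ)). At ρ = 0.3 this is SD × √1.4 = 1.183 SD. For a difference of δ × SD the noncentrality is δ / √(2(1 − ρ)) × √n. Power is the probability that a noncentral t exceeds the two-sided 5% critical value. Ranges run from n − 2 degrees of freedom (crossover with a period effect) to n − 1 (paired t).

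**The plan's own figures.**
- n = 20, δ = 0.79: noncentrality 0.79 / 1.183 × √20 = 2.986; critical values 2.101 (18 df) and 2.093 (19 df); power 80.6–80.8%. The figure reproduces.
- n = 40, δ = 0.54: noncentrality 0.54 / 1.183 × √40 = 2.886; power 80.3–80.4%. This reproduces too, and does not depend on the split between cohorts.

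**Power for 0.79 SD at assumed Cohort B sizes.**

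| Assumed n | ρ = 0.3 (stated minimum) | ρ = 0.5 | ρ = 0.7 |
|---|---|---|---|
| 19 | 78.3–78.6% | 90.0–90.2% | 98.7% |
| 15 | 66.7–67.2% | 80.7–81.2% | 95.4–95.6% |
| 10 | 45.9–47.0% | 59.2–60.6% | 80.6–81.8% |
| 5 | 18.6–21.2% | 23.9–27.5% | 35.4–41.4% |

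At the stated minimum correlation, 80% is lost as soon as n falls below 20. If the total were exactly 40 with most subjects in Cohort A, Cohort B could have at most 19. The correlation needed to restore 80% at 0.79 SD is about 0.33 for n = 19, 0.48–0.49 for n = 15, 0.69–0.70 for n = 10 and 0.89–0.91 for n = 5.

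**What is done with Cohort B's primary endpoints.**

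| Endpoint | As primary (SAP 8.1) | Elsewhere in the SAP |
|---|---|---|
| Activity (AUS/NZ only) | Listed | Summarised and modelled as secondary (8.2, BioStamp) |
| Pupillometry | Listed | Summarised and modelled as secondary (8.2, Pupillary Diameter) |
| DCFS | Listed | No secondary analysis |
| Waking EEG | Separate plan, not among the documents reviewed | – |

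A by-subject listing makes no treatment comparison. For the first three endpoints as primary endpoints, no power statement applies, whatever n turns out to be.

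**The case against.** The strongest reply is that the sentence is conditional and true: 20 subjects do give 80%. SAP 4.3 presents it as support for a size fixed on practical grounds, with no formal testing, and it has already dropped the protocol's 20/20 allocation. The recruitment shift is disclosed under changes from the protocol, repeated in 4.1, and followed through in 8.1 with its reason. All of this stands. It makes the matter one of wording and limits the harm, because anyone who reads 2.1 and 8.1 will not be misled. The practical basis also largely explains the remarks in SAP 8 and 8.2 that the study was not powered on statistical assumptions.

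It does not rescue the sentence for Cohort B. The condition is one that the SAP itself expects not to be met, and the sentence names primary endpoints for each cohort. SAP 2.1 leaves primary analyses out of its list of Cohort B tables but never says that the comparison in SAP 3 has been dropped.

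It is also fair to say that the power table rests on assumed n and correlation, and measures nothing that a listing does. It shows how quickly the stated figure erodes. The absence of a comparison needs no such assumption.

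A reader might infer three stronger points that the documents do not support:
- **That the statement is wrong for Cohort A.** It remains true for any n of 20 or more; a larger cohort only makes it conservative.
- **That Cohort B's activity and pupillometry data are never summarised or compared.** SAP 2.1 and 8.2 include Cohort B in the secondary analyses.
- **That the secondary models cannot yield a Cohort B effect.** SAP 8 presents efficacy data by cohort, and the pupillometry model does not say whether cohorts are pooled; only the BioStamp model refers to all subjects. The point is open for pupillometry.

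**Conclusion.** The per-cohort power statement should not stand for Cohort B's primary endpoints. This rests on two grounds. First, this SAP makes no primary treatment comparison on activity, pupillometry or DCFS; that follows from SAP 8.1 alone. Second, at the stated minimum correlation any Cohort B smaller than 20 falls short of 80% for 0.79 SD, from 78% at 19 subjects down to 19–21% at 5. The second ground depends on an assumed n and on the correlation staying near 0.3; at 0.5, 15 subjects would be enough.

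SAP 3 is out of step in the same way, since it still states the Cohort B comparison as part of the primary objective. The arithmetic in 4.3 is sound, and the pooled figure is unaffected. Nothing is concluded about waking EEG or FERT, whose plans are separate. This is a statement to correct in the SAP, not an error of analysis.

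**What to change.** In SAP 4.3, limit the 80% power and 0.79 SD statement to a cohort that reaches 20 subjects, which is expected to be Cohort A. Remove it for Cohort B's primary endpoints, with a pointer to 2.1 and 8.1. Leave the figure for 40 pooled subjects (0.54 SD) unchanged. Optionally, give Cohort A's detectable difference at its expected size: with 80% power and correlation 0.3, this is 0.69, 0.63 or 0.58 SD for an assumed 25, 30 or 35 subjects.

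In SAP 2.1 or 3, state that this SAP makes no primary treatment comparison for Cohort B on activity, pupillometry or DCFS. Say that these are listed only as primary endpoints, that activity and pupillometry are also summarised and modelled as secondary endpoints, and that waking EEG is governed by its separate plan. Check the wording against that plan before it is final.

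The cost is a few sentences, with no extra subjects, data or analyses. The downside is a less favourable stated position for Cohort B.
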